9.3.3 Covariates

Table 9.3.3:1 Covariates related to patient profile

	Data from Medical Charts	Data Measured at Study Visit
Age, gender, ethnicity.	X	
Height & weight (BMI auto-calculated) *	X	
Smoking history.	X	
Pulmonary function test - Spirometry # *	X	
Bronchodilator test # * (FEV ₁ increase, absolute values).	X	
Episodes of wheezing in exacerbations.	X	
COPD diagnosis (year)	X	

History of asthma (yes/no) and year of diagnose	X	
History of atopy (yes/no).	X	
Blood Eosinophilia (number of eosinophils and %) *	X	
Immunoglobulin E (Ig E) *	X	
Current COPD treatment (including ICS: start and stop dates, dose, reason) §	X	
History and details of Exacerbations (last 2 years).	X	
History of antibiotics and oral corticosteroids for COPD	X	
Comorbidities (COTE index)	X	
Concomitant medication.	X	
COPD GesEPOC 2017 phenotypes	X	
GOLD 2017 spirometric classifications (1, 2, 3, 4).	Auto-calculated	
GOLD 2017 patient groups (A, B, C, D).	Auto-calculated	
BODEx (BMI / % FEV ₁ / mMRC / severe Exacerbations)	Auto-calculated	
Breathlessness based on mMRC score.		X
QoL: CAT - COPD Assessment Test		X

* Last measure available

available in medical charts <12 months

§ Not including possible changes or new prescriptions done at study visit

The covariates will also be included as independent variables for multivariable analysis: COPD phenotypes, GOLD group, BODEx index, mMRC score and CAT – COPD Assessment Test.

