7. GENERAL CONSIDERATIONS

The design of the study imposes an only one visit to be performed that will coincide with one of those performed by the patients as part of routine follow-up of their disease, without interfering with usual clinical practice of the investigator.

Data will be obtained from patient medical records and during the study visit. Most of data will be available in the charts but as a routine clinical practice, some data could be missing. Data will be collected through an eCRF, which will include all the study variables.

The Investigator will enter the patient following the user guide during the study visit will fill in the CAT – COPD Assessment Test and mMRC data electronically into the eCRF system.

Boehringer Ingelheim reserves the right to discontinue the study overall or at a particular study site at any time for the following reasons:

1. Failure to meet expected enrolment goals overall or at a particular study site
2. Emergence of any efficacy/safety information that could significantly affect continuation of the study
3. Violation of the study protocol, or the contract by a study site or investigator, disturbing the appropriate conduct of the study

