8.4 Missing data

Missing data will not be imputed, except in those variables described in their scoring system.

According to general analysis, if patients have missing values for an outcome, those patients will be excluded for that outcome's analysis.

Document: \\bcnfs02\general\Hdmgener\MEDICAL AFFAIRS 28.02.2017 actualizada\8. SRO ESTUDIOS\RESPIRATORIO\1237-0070 NIS OPTI\11 - Clinical Trial Report\SAP\SAP - V 1.0\SAP OPTI version1.0 29052019.docx

Author:

Version Number: 1.0

Version Date: [29MAY2019]

Template No.: RWI_TP_BIOS0013 Revision 1

Reference: RWI_WI_BIOS0015

Effective Date: 15Jun2018

Copyright © 2018 All rights reserved. The contents of this document are confidential and proprietary to Holdings Inc. and its subsidiaries. Unauthorized use, disclosure or reproduction is strictly prohibited.

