16.1.3.1 Current treatment with ICS

Main variable will be presented according to the presence or not of moderate/severe exacerbations in the previous 365 days.

The use of ICS will be analyzed using number of patients in each category and percentages (absolute and relative frequencies) and 95% confidence intervals will be provided based on Wald's (Normal Approximation) method for each group. Percentages will be compared using Chi-Square test or Fisher's Exact test.

Logistic regression will be used to assess the independent contribution of clinical and demographic factors to the estimation of the proportion of patients with COPD who use ICS inadequately. First, univariate and second, multiple logistic regression (MLR) methods will be used to investigate the impact of the following explanatory covariates (patient and disease characteristics) on ICS use.

Potential covariates are:

- Age
- gender
- Smoking history
- Number of exacerbations in the previous year.
- History of asthma (yes/no)
- History of atopy (yes/no)
- COTE index
- COPD GesEPOC 2017 phenotype

Document: \\bcnfs02\general\Hdmgener\MEDICAL AFFAIRS 28.02.2017 actualizada\8. SRO ESTUDIOS\RESPIRATORIO\1237-0070 NIS OPTI\11 - Clinical Trial Report\SAP\SAP - V 1.0\SAP OPTI version1.0 29052019.docx

Author:

Version Number: 1.0

Version Date: [29MAY2019]

Template No.: RWI_TP_BIOS0013 Revision 1

Reference: RWI_WI_BIOS0015

Effective Date: 15Jun2018

Copyright © 2018 All rights reserved. The contents of this document are confidential and proprietary to Holdings Inc. and its subsidiaries. Unauthorized use, disclosure or reproduction is strictly prohibited.

- GOLD 2019 spirometric classifications (1, 2,3, 4)
- GOLD 2019 patient groups (A, B, C, D)
- mMRC score
- CAT - COPD Assessment Test

Backward selection procedures will be applied to generate the final MLR models which consider only covariates in the selection procedure with a p-value <0.1 in the corresponding univariate logistic regression analysis, using inadequate ICS use (yes/no) as response variable. A p-value <0.05 will be used for the covariates to stay in the model in a backward elimination step. Continuous variables can be replaced by categorical variables. Parameters estimated, exp(B) and C95% Wald Confidence Limits for OR will be presented.

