COPD GesEPOC 2017 phenotypes	non-exacerbator, mixed COPD - asthma syndrome (ACOS), exacerbator with emphysema exacerbator with chronic bronchitis		(ref)	
GOLD 2019 spirometric classification	Gold 1 – Mild Gold 2 – Moderate Gold 3 – Severe Gold 4 – Very severe		(ref)	
GOLD 2019 patient groups (A, B, C, D)	Patient A Patient B Patient C Patient D		(ref)	
CAT score (cat)	CAT <10: Low impact of COPD. CAT ≥10: Medium / high impact of COPD		(ref)	
mMRC score	Grade 0 Grade 1 Grade 2 Grade 3 Grade 4		(ref)	
Number of eosinophils (%)	<2% ≥ 2%		(ref)	

Document: \\bcnfs02\general\Hdmgener\MEDICAL AFFAIRS 28.02.2017 actualizada\8. SRO ESTUDIOS\RESPIRATORIO\1237-0070 NIS OPTI\11 - Clinical Trial Report\SAP\SAP - V 1.0\SAP OPTI version1.0 29052019.docx

Author:

Version Number: 1.0

Version Date: [29MAY2019]

Template No.: RWI_TP_BIOS0013 Revision 1

Reference: RWI_WI_BIOS0015

Effective Date: 15Jun2018

Copyright © 2018 All rights reserved. The contents of this document are confidential and proprietary to Holdings Inc. and its subsidiaries. Unauthorized use, disclosure or reproduction is strictly prohibited.

Variable	Category	Inadequate use of ICS	Odds-Ratio (OR)	p-value
Inmunoglobulin E (UI/ml)	<= 100 UI/ml >100 UI/ml		(ref)	
Presence of exacerbations in previous 2 years	None 1-2 exacerbations 3-4 exacerbations 5+ exacerbations		(ref)	
Presence of moderate/severe exacerbations in previous 2 years	None 1-2 moderate/severe exacerbations 3-4 moderate/severe exacerbations 5+ moderate/severe exacerbations		(ref)	
Presence of severe exacerbations in previous 2 years	None 1-2 severe exacerbations 3-4 severe exacerbations 5+ severe exacerbations		(ref)	
Presence of exacerbations in previous year	None 1-2 exacerbations 3-4 exacerbations 5+ exacerbations		(ref)	
Presence of moderate/severe exacerbations in previous year	None 1-2 moderate/severe exacerbations 3-4 moderate/severe exacerbations 5+ moderate/severe exacerbations		(ref)	
Presence of severe exacerbations in previous year	None 1-2 severe exacerbations 3-4 severe exacerbations 5+ severe exacerbations		(ref)	
Antibiotics for COPD exacerbations	No Yes		(ref)	
Oral corticosteroids for COPD exacerbations	No Yes		(ref)	
Type of ICS	ICS alone LABA + ICS LABA + LAMA + ICS			

Inadequate use of ICS: use of ICS without moderate/severe exacerbations in the previous year in patients.

Table 26. Multivariate logistic regression model of inadequate use of ICS (use of ICS without moderate/severe exacerbations in the previous year)

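### Backward selection in SAP 16.1.3.1 and 16.2.2 has no missing-covariate rule and no refit, so the final models may rest on a reduced subset of unreported size; Table 25 also lists 'Type of ICS', which is undefined for non-users

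*SAP*

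**What the plan says.** **Selection.** SAP 16.1.3.1 names 12 potential covariates for inadequate ICS use, among them the spirometric GOLD 1-4 class. The final model starts from a univariate screen: "Backward selection procedures will be applied to generate the final MLR models which consider only covariates in the selection procedure with a p-value <0.1". Then: "A p-value <0.05 will be used for the covariates to stay in the model in a backward elimination step". The age-subgroup models reuse this procedure. SAP 16.2.2 repeats it for the negative binomial models of exacerbation counts, with the primary-analysis covariates less the prior-year count.

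**Missing data.** SAP 8.4 states: "Missing data will not be imputed, except in those variables described in their scoring system". Its exclusion rule concerns outcomes: "if patients have missing values for an outcome, those patients will be excluded for that outcome's analysis". Neither document says what happens to a patient with a missing covariate, or whether the selected model is refitted.

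**Expected gaps.** SAP 7 says of the data: "Most of data will be available in the charts but as a routine clinical practice, some data could be missing". The footnote to the covariate table in protocol 9.3.3 limits spirometry and the bronchodilator test to results "available in medical charts <12 months".

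**Candidates.** Table 25, the shell for the univariate step, goes beyond the 16.1.3.1 list. Its extra rows include BMI, BODEx, eosinophils, IgE and type of ICS. Protocol 9.3.3 names BODEx as an independent variable for the multivariable analysis; the 16.1.3.1 list omits it.

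**Reporting.** The shells of Tables 26, 27 and 32 have no place for the number of patients in the model.

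**The concern.** Automated backward selection normally fixes its sample at the first step: patients with a gap in any starting candidate are set aside and do not return when that candidate is eliminated. A variable that ends up outside the final model can thus decide who is in it. SAP 7.3 specifies SAS 9.4, where this is the usual behaviour for logistic selection. If elimination is done by hand, patients may come back as variables leave and N drifts between steps. The SAP does not say which applies.

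At stake are the precision of the odds ratios and rate ratios, and knowing whom they describe. Two analysts following this SAP could start from different candidate sets, use different patients, and produce tables that would not show the difference.

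Type of ICS is a separate problem. It exists only for ICS users, while the response is itself a form of ICS use. No assumption about chart quality is needed to see that it cannot serve as a predictor there.

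**Working it through.** **Inputs from SAP 4.2:** 900 evaluable patients; 66% non-exacerbators; 61% of these on ICS; 10% allowance for inconsistent, incomplete or missing data. Completeness per covariate is not given anywhere and is assumed below.

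**The plan's own figures reproduce.** 0.66 × 0.61 = 0.403, or about 40%. The half-width is 1.96 × √(0.40 × 0.60 / 900) = 0.032, giving 36.8% to 43.2%. 900 / 0.90 = 1,000. The plan states no N for any multivariable model.

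**Base for the regression.** SAP 16.1.3.2 presents inadequate use only for patients without exacerbations in the previous year: 900 × 0.66 = 594, of whom 594 × 0.61 ≈ 362 are on ICS and about 232 are not.

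**Loss from spirometry alone.** Remaining n = 594 × completeness; interval width factor = √(594 / n).

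- 90% complete: n = 535, factor √(594/535) = 1.05.
- 70% complete: n = 416, factor √(594/416) = 1.20.

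For the negative binomial models on the full analysis set (FAS), the same range leaves 900 × 0.7 = 630 to 900 × 0.9 = 810, with the same factors. For the age-subgroup models, if three equal groups are assumed (Table 27 shows three), each starts at 594 / 3 = 198 and keeps 139 to 178.

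**If eosinophils and IgE were also starting candidates.** Assume eosinophils 60-90% and IgE 10-40% complete.

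- Independent gaps: 594 × 0.7 × 0.6 × 0.1 = 25, up to 594 × 0.9 × 0.9 × 0.4 = 192 (factors 4.9 and 1.8).
- Fully overlapping gaps, so that IgE alone sets the limit: 594 × 0.1 = 59, up to 594 × 0.4 = 238 (factors 3.2 and 1.6).

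This case requires Table 25 to be taken as the candidate list and both variables to pass p<0.1.

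**Type of ICS.**

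- Exacerbation-free cohort: requiring a value leaves only the 362 ICS users, and by the Table 25 definition all of them are inadequate users. The response has one level, so no odds ratio can be estimated.
- Full FAS: there are 900 − 594 = 306 exacerbators. If 40-90% of them use ICS (assumed), 122 to 275 join the 362, giving 485 to 638 patients; 46% to 29% of the 900 are lost. A model runs, but it asks which ICS users are free of exacerbations, not who is given ICS without them.

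**The case against.** The strongest defence is that the written candidate list is the one in 16.1.3.1, and on that list the loss is moderate. A reader might infer that the final model will be fitted on a small, selected subset. The documents do not support that: they give no missingness rate, and the range from 25 to 238 patients needs candidates that appear only as rows in a table shell. At 10% completeness IgE would be screened in about 59 patients, so it would have little chance of passing p<0.1.

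A reader might also infer that the odds ratios will be biased. That is conditional. Complete-case logistic odds ratios are not generally biased when missingness depends only on the model covariates or only on the outcome. If IgE is ordered for suspected asthma, the link runs largely through asthma history, which is a listed candidate.

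Nor does type of ICS stop every model. In the exacerbation-free cohort it gives no valid univariate p-value, so it should fail the screen; in the full FAS a model can be fitted. It is also the only categorical row in Table 25 without a reference level, which may mean it was meant as description.

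Further points stand. The 594 is already net of the 10% allowance, so part of the loss may be counted twice. Entry requires a previously confirmed spirometric diagnosis, although not one from the last 12 months. Tables 7 and 10 print missing counts and Table 25 prints n/N. P-values are declared descriptive in SAP 8.2, and the primary proportion is untouched.

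None of this supplies a missing-covariate rule, a refit or a model N.

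**Conclusion.** The concern holds in a limited form. With a p<0.1 screen, backward elimination, no imputation and no refit, the final logistic and negative binomial models may rest on a reduced and selected subset whose size the planned tables do not show. On the 16.1.3.1 list, with spirometry assumed 70-90% complete, the cost is moderate: about 59 to 178 of 594 patients lost (594 − 535 and 594 − 416). Greater loss depends on eosinophils and IgE becoming candidates, which the SAP text does not say but its Table 25 leaves open. Complete-case fitting is itself the implied default, not a stated rule.

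The type-of-ICS row is wrong as a predictor whatever the completeness: it cannot be estimated in the exacerbation-free cohort and changes the question in the full FAS.

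This should be corrected, but it does not threaten the primary result.

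**What to change.** 1. Delete type of ICS from Table 25. State in 16.1.3.1 that the multivariable candidates are its own list plus BODEx, as protocol 9.3.3 requires, and that eosinophils and IgE are univariate rows only. BODEx needs little new data: FEV1 is already required for GOLD 1-4, mMRC is taken at the visit, and the remaining parts are BMI and severe exacerbations.
2. In 16.1.3.1 and 16.2.2, state that after selection the final logistic and negative binomial models are refitted on all patients complete for the retained covariates, and that this fit is the one reported.
3. Print N used and N dropped under Tables 26, 27 and 32.

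The cost is SAP wording and one extra run per model. Eosinophils and IgE are not adjusted for. The refit recovers patients for the retained covariates but does not undo a selection made on the smaller set. The SAP is dated 29 May 2019, after the planned end of data collection in April 2019, so covariate completeness could be counted before modelling, replacing the assumed ranges above.

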8.3 Adjustments for Covariates and Factors to be Included in Analyses

For some of the endpoints, multivariate analyses will be performed using the following covariates and factors. For details of their inclusion in the models, see the specific analysis section. Fixed variables are:

- Age
- Gender

Some optional variables are:

- Smoking history
- Number of exacerbations in the previous year.
- FEV₁ (%) or COPD severity
- FVC (%)
- COPD Risk
- COPD Phenotype
- Gold 2019 Classification A, B, C, D
- Comorbidities as asthma and/or atopy
- CAT category

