Additionally, logistic regression model will be performed for each age subgroup, using the same procedure described in the previous paragraph. Age subgroups will be adjusted according to the distribution of patients.

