16.2.2 Moderate-to-severe exacerbations in COPD

This analysis consists of the number (count) of moderate-to-severe exacerbations in the previous 1 and 2 years previous to the study visit in COPD patients according to ICS use at time of study visit.

Document: \\bcnfs02\general\Hdmgener\MEDICAL AFFAIRS 28.02.2017 actualizada\8. SRO ESTUDIOS\RESPIRATORIO\1237-0070 NIS OPTI\11 - Clinical Trial Report\SAP\SAP - V 1.0\SAP OPTI version1.0 29052019.docx

Author:

Version Number: 1.0

Version Date: [29MAY2019]

Template No.: RWI_TP_BIOS0013 Revision 1

Reference: RWI_WI_BIOS0015

Effective Date: 15Jun2018

Copyright © 2018 All rights reserved. The contents of this document are confidential and proprietary to Holdings Inc. and its subsidiaries. Unauthorized use, disclosure or reproduction is strictly prohibited.

Patients with missing data related to exacerbations will be excluded from the analysis and number of missing values will be presented.

The objective is to describe the number (total count) of moderate-to-severe exacerbations in one and two years previous to the study visit according to ICS treatment at the time of study visit.

Results will be analyzed with measures of central tendency (mean and median), variability/dispersion (standard deviation and interquartile ranges) and ranges. The number of moderate-to-severe exacerbations will be analyzed using Mann-Whitney U test or Kruskal-Wallis non-parametric tests.

After that, at exploratory level, negative binomial regressions will be used for modelling discrete-count variables, not continuous and limited to non-negative values as the number of moderate-to-severe exacerbations (counts), both for first and second previous years. Covariates included in the model will be those used also in primary analysis, excluding the number of exacerbations in the previous year.

Backward selection procedures will be applied to generate the final model which consider only covariates in the selection procedure with a p-value <0.1 in the corresponding univariate analysis, using number of exacerbations as response variable. A p-value <0.05 will be used for the covariates to stay in the model in a backward elimination step. Continuous variables can be replaced by categorical variables.

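### The logistic regression asks for each factor's independent contribution, but a univariate p<0.1 screen decides which factors may enter, so a masked factor is likely to be dropped before any adjustment

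*SAP*

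**What the plan says.** SAP 16.1.3.1 gives the aim: "Logistic regression will be used to assess the independent contribution of clinical and demographic factors" to the proportion of patients using ICS inadequately. Protocol 9.7.2 gives the same aim. The section lists twelve potential covariates: age, gender, smoking, previous-year exacerbation count, asthma, atopy, COTE, GesEPOC phenotype, GOLD 1-4, GOLD A-D, mMRC and CAT.

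The final models "consider only covariates in the selection procedure with a p-value <0.1 in the corresponding univariate logistic regression analysis". Elimination follows: "A p-value <0.05 will be used for the covariates to stay in the model in a backward elimination step". No step brings back a covariate that failed the screen.

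The rule is used again in two places. For Table 27, a "logistic regression model will be performed for each age subgroup, using the same procedure described in the previous paragraph". For the exploratory negative binomial models in 16.2.2, selection applies to models "which consider only covariates in the selection procedure with a p-value <0.1 in the corresponding univariate analysis".

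SAP 8.3 bears on two covariates. Under "Fixed variables are" it lists age and gender, but it adds: "For details of their inclusion in the models, see the specific analysis section". Section 16.1.3.1 then lists both as potential covariates and forces neither.

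**The concern.** Whether a factor contributes given the others is a conditional question. The univariate test asks whether the factor is associated with the response when everything else is ignored. The two answers differ when covariates are correlated, and some of these must be: SAP 7.2.12 builds GOLD A-D from exacerbations, mMRC and CAT.

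Take a factor that raises inadequate use and is negatively correlated with another factor that also raises it. Its crude association is pulled towards zero. If it fails the screen, backward elimination cannot restore it. Table 26 then has no estimate for it, and a reader may take its absence to mean no independent contribution. The partner's odds ratio is also biased, because it is not adjusted for the missing factor.

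**Working it through.** **1. The plan's own figures.** SAP 4.2 assumes 900 evaluable patients and a proportion of 40%: 0.40 ± 1.96 × √(0.40 × 0.60/900) = 0.40 ± 0.032, or 36.8% to 43.2%, as stated. Allowing for 10% dropout, 900/0.9 = 1,000, as stated. The documents give no figure for the regression.

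**2. Size of the model's cohort.** SAP 4.2 takes 66% as non-exacerbators, of whom 61% are on ICS.
- Cohort of SAP 16.1.3.2 (no exacerbation in the previous year): 900 × 0.66 = 594.
- Smaller response class, not on ICS: 594 × 0.39 ≈ 232.

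**3. Why the screen can miss a real factor.** For two standardised covariates with adjusted log odds ratios b1 and b2 and correlation ρ, the crude log odds ratio of the first is approximately b1 + ρ·b2. The crude standard error is about 1/√(594 × 0.61 × 0.39) = 0.084. In the joint model it is about 0.084/√(1 − ρ²).

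Assume odds ratios per SD of 1.3 (b1 = 0.262) and 1.5 (b2 = 0.405), with ρ = −0.3.
- Crude: 0.262 − 0.3 × 0.405 = 0.141 (odds ratio 1.15), z = 0.141/0.084 = 1.67. The chance of passing two-sided p<0.1 is about 51%.
- Joint: standard error 0.088, z = 0.262/0.088 = 2.98. The chance of p<0.05 is about 84%.

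**4. Simulation of the whole procedure.** Settings: n = 594, about 60% on ICS, eight further noise candidates, univariate p<0.1, then backward elimination at p<0.05. Two sets of 300 runs per setting were made, so one percentage near 50% has a standard error of about 3 points. Entries are the percentage of runs that detect the first factor, full model versus SAP route.

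| Factor OR | Second-factor OR | ρ | Set 1 | Set 2 |
|---|---|---|---|---|
| 1.3 | 1.5 | 0 | 86 vs 85 | 87 vs 87 |
| 1.3 | 1.5 | −0.2 | 86 vs 70 | 80 vs 60 |
| 1.3 | 1.5 | −0.3 | 80 vs 45 | 79 vs 52 |
| 1.3 | 1.5 | −0.5 | 75 vs 19 | 78 vs 17 |
| 1.3 | 2.0 | −0.3 | 79 vs 13 | 81 vs 17 |
| 1.5 | 2.0 | −0.3 | 100 vs 69 | 99 vs 73 |

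With ρ = +0.3 and effects in the same direction there was no loss (85 vs 85). When the masked factor was dropped, its partner's mean odds ratio fell from a true 1.5 to 1.42 at ρ = −0.3 and to 1.35 at ρ = −0.5.

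**5. Full and half masking.** Full masking means b2 = −b1/ρ, so the crude effect is zero. A separate simulation (1,000 runs per setting; |ρ| 0.3 to 0.7, odds ratio 1.3 to 1.5, n = 594 and 900) gave these results.
- Full masking: the screen was passed in 9-11% of runs, which is its nominal error rate. The joint model detected the factor in 59-100%. Going from 594 to 900 patients did not raise the pass rate.
- Half masking: passed in 43-91%, detected jointly in 57-100%.

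**6. Whether the screen is needed for model size.** Parameters: age 1, gender 1, smoking 2, asthma 1, atopy 1, COTE 1, phenotype 3, GOLD 1-4 3, mMRC as categories 4, CAT 1; total 18.
- Overall model: 232/18 ≈ 13 patients in the smaller class per parameter, before missing covariates.
- Age subgroups, assuming three equal groups: 232/3 ≈ 77, and 77/18 ≈ 4 per parameter.

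**The case against.** Several stronger readings are tempting and are not supported.

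- *A masked factor never reaches the model.* This is true only of a factor that fails the screen. Some pass by chance under full masking, and many pass under half masking.
- *Nothing in the plan protects any covariate.* Age and gender may be exempt under SAP 8.3. Because 8.3 defers to 16.1.3.1, which forces neither, their status is unclear. The other ten covariates are screened on either reading.
- *The loss is known to be large.* No document gives a correlation or an effect size. Severity measures such as spirometric grade, mMRC and CAT could well correlate positively and act in the same direction, and then nothing is lost. The assumed odds ratios are also per SD. For a yes/no factor with an assumed prevalence of 15-30%, 1.5 per SD means a yes/no odds ratio of about 3.1 to 2.4, and 2.0 means about 7.0 to 4.5, so the most severe rows need strong partners.
- *The procedure manufactures false findings.* With 11 null candidates it keeps at least one in 44% of runs. Eleven independent 5% tests in a full model give 1 − 0.95^11 = 43%, so this is not a fault of the screen.
- *All twelve listed covariates could simply be fitted together.* The exacerbation count overlaps the response in Table 25 and is essentially constant in the 16.1.3.2 cohort. GOLD A-D duplicates mMRC and CAT.

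It is also fair to say that the study is descriptive, that SAP 8.2 calls its p-values descriptive, that the selection rule is prespecified and that Table 25 keeps crude odds ratios visible. This limits the consequence. It does not remove the mismatch, because crude odds ratios are what masking distorts, and here p-values decide which adjusted estimates are printed.

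**Conclusion.** The concern holds in a limited form. The aim in SAP 16.1.3.1 and protocol 9.7.2 is conditional and the entry screen is marginal, so the procedure can discard a factor with a real adjusted effect and leave its partner's odds ratio unadjusted for it. The cost ranges from nothing, without opposing correlation, through power of about 80% falling to about 45-52% at the assumed ρ of −0.3 (odds ratios 1.3 and 1.5 per SD), to a pass rate of about 10% under full masking. All of this rests on assumed correlations and effects, and on 594 patients with complete covariates.

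The harm is confined to the adjusted odds ratios and to which factors are reported as independent. The primary proportion is unaffected. The negative binomial models share the screen, but they are exploratory and 16.2.2 does not claim independent contribution for them. This is a cheap improvement and does not put the study's main result in doubt.

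**What to change.** - **Overall logistic model (SAP 16.1.3.1, Table 26).** Delete the univariate p<0.1 entry condition. Present first one prespecified model with age, gender, smoking, asthma, atopy, COTE, phenotype, GOLD 1-4, mMRC and CAT, each in one form, with sparse categories merged. Leave out the previous-year exacerbation count and GOLD A-D. Print every adjusted odds ratio with its 95% CI, and the number of complete cases. Any backward-selected model follows, labelled exploratory. Table 25 can stay as a univariate description.
- **Negative binomial model (16.2.2, Table 32).** Do the same, printing rate ratios. Leave out the exacerbation count, which 16.2.2 already excludes, and GOLD A-D, because both are built from the response.
- **Age subgroups (Table 27).** Do not carry the full model over. Use a short prespecified covariate set.
- **SAP 8.3.** Reconcile it with 16.1.3.1 on whether age and gender are always in the model.

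No new data or patients are needed. The downsides are a longer table, somewhat wider intervals and loss of any patient with a missing covariate, because SAP 8.4 rules out imputation. That loss could matter: SAP section 7 expects gaps in the charts, and protocol Table 9.3.3:1 limits spirometry to values less than 12 months old.
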